In a subject who has a baseline bone marrow biopsy showing bone marrow involvement with lymphoma or does not have a baseline bone marrow examination, declaration of an on-study CR requires bone marrow biopsy documentation of the absence of bone marrow lymphoma. In a subject who has a baseline bone marrow biopsy showing no evidence of lymphoma, declaration of an on-study CR does not require bone marrow examination as long as other criteria for CR are met.

Definitions of Tumor Response and Progression

Responses will be categorized as complete response (CR), partial response (PR), stable disease (SD), or progressive disease (PD). In addition, a response category of not evaluable (NE) is provided for situations in which there is inadequate information to otherwise categorize response status.

The best overall response will be determined. The best overall response is the best response recorded from the start of study drug until PD/recurrence (taking as reference for PD the smallest measurements recorded since study drug started). Subjects with a best overall response of NE will be included in the denominators in calculations of tumor response rate.

Response Categories

Complete Response

To satisfy criteria for CR, all of the following criteria must be met:

- No evidence of new disease
- Regression of all index nodal lesions to normal size (≤ 1.5 cm in the LD for nodes that were considered large at baseline and ≤ 1.0 cm in the LD and ≤ 1.0 cm in the LPD for nodes that were considered small at baseline) (see Nodal Index Lesions section for definitions of large and small nodes)
- Regression to normal of all nodal non-index disease

- Disappearance of all detectable extra-nodal index and non-index disease
- Normal spleen and liver size by imaging studies, no hepatic or splenic lymphoma nodules, and no new liver or spleen enlargement
- Morphologically negative bone marrow based on an adequate unilateral core biopsy if the sample is indeterminate by morphology, it should be negative by immunohistochemistry
- If PET performed (not required), no evidence of residual disease

Partial Response

To satisfy criteria for PR, all of the following criteria must be met as noted below:

- No evidence of new disease
- A $\geq 50\%$ decrease from baseline in the SPD of the index lesions
- No increase in the size of non-index disease
- No increase in the size of the liver or spleen and no new liver or spleen enlargement

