 - Increase from the nadir by $\geq 50\%$ in the LD of an individual node or extra-nodal mass that now has an LD of >1.5 cm and an LPD of > 1.0 cm
- Unequivocal increase in the size of non-index disease
- If PET performed (not required):
 - The appearance of any new lesion compatible with lymphoma with confirmation by other radiographic or histological modalities
 - The reappearance of any activity in a pre-existent lesion that meets size criteria for a new lesion on CT

Note: If there is uncertainty regarding whether there is definitive lymphoma progression, the subject should continue study drug and remain under close observation (eg, evaluated at scheduled intervals). In particular, worsening of constitutional symptoms in the absence of objective evidence of worsening lymphoma will not be considered definitive disease progression; in such subjects, both lymphoma -related and non-lymphoma -related causes for the constitutional symptoms should be considered. Transient worsening of disease during temporary interruption of study drug(s) (eg, for intercurrent illness) may also not indicate definitive disease progression. In these instances, CT/MRI should be attempted in order to document whether definitive disease progression has occurred. If subsequent evaluations suggest that the subject has experienced persistent definitive disease progression, then the date of progression will be the time point at which progression was first objectively documented.

Non-Evaluable

In a subject who does not have evidence of PD, the occurrence of any of the following conditions indicates a response status of NE:

- There are no images or inadequate or missing images.

Note: A time-point will be considered to have a response of NE if any index lesion is missing. PD may be assigned at any time point regardless of the extent of missing index or non-index lesions. Missing non-index lesions will not impact the ability to assess for response or disease progression.

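### The lymphoma criteria say missing non-index lesions do not matter, yet their own definition of complete response depends on those lesions, so the same scan can be classed as CR, not CR, or NE

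*Protocol*

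**What the plan says.** Protocol Appendix 5 defines lymphoma response. Under Non-Evaluable, a subject without PD is NE at a time point where "There are no images or inadequate or missing images". The note beneath adds three rules:

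- Index lesions: "A time-point will be considered to have a response of NE if any index lesion is missing".
- Progression: "PD may be assigned at any time point regardless of the extent of missing index or non-index lesions".
- Non-index lesions: "Missing non-index lesions will not impact the ability to assess for response or disease progression".

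The response categories in the same appendix refer to non-index disease directly:

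- CR is conjunctive: "To satisfy criteria for CR, all of the following criteria must be met". One criterion is that all nodal non-index disease returns to normal. Another is "Disappearance of all detectable extra-nodal index and non-index disease".
- PR, also conjunctive, includes "No increase in the size of non-index disease".
- PD can rest on "Unequivocal increase in the size of non-index disease" alone, as one of several sufficient findings.

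Up to 6 index and up to 6 non-index lesions are recorded at baseline. Non-index disease may include measurable, abnormal lesions that were simply not chosen as index lesions. Best overall response (BOR) is the best response recorded from the start of study drug until progression or recurrence.

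SAP 6.1.1.2 counts NE as nonresponse and keeps it in the denominator. SAP 6.1.2.2 tabulates BOR by category, study group and dose level. The SAP has no rule for missing non-index lesions.

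**The concern.** A criterion that demands the disappearance of a lesion cannot be met by a lesion nobody looked at. The note tells the assessor that such a gap has no bearing on response, so an assessor who follows it can record CR with known baseline disease unaccounted for. Because BOR keeps the best category recorded, a single incompletely assessed visit is enough to fix a subject's BOR as CR.

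This also sits badly with the appendix's own approach to bone marrow. If the marrow was involved or not examined at baseline, CR requires a biopsy showing no lymphoma. There, absence of disease must be shown and is not presumed.

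At stake is the count of lymphoma complete responses in the BOR table, and whether two assessors with the same scans would reach the same category.

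**Working it through.** The plan states no figure on this point, so there is none to reproduce. The check sets the rules side by side for one data pattern.

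**Pattern.** All index lesions were assessed and have regressed to normal. There is no new disease. Liver, spleen and marrow criteria are met. One non-index lesion present at baseline was not assessed at this visit.

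**Three readings of that pattern under Appendix 5:**

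1. *The note on missing lesions.* No index lesion is missing, so the note does not make the visit NE. The missing non-index lesion is said to have no effect. Result: CR stands.
2. *The CR list.* All criteria must be met. The nodal or the extra-nodal non-index criterion, depending on the lesion, is unverified. Result: CR is not established.
3. *The general NE condition.* If the lesion was not assessed because images were inadequate or missing, the visit meets that condition in the absence of PD. Result: NE.

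Nothing in Appendix 5 ranks these rules, and nothing in it lowers CR to PR when non-index disease is unassessed.

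**Comparison within the protocol.** RECIST Table 1 in Appendix 3 covers the analogous solid-tumor case. Target CR with non-target lesions not evaluated and no new lesions gives PR. The question-and-answer section of that appendix likewise says that one unexamined non-target lesion prevents a claim of CR. RECIST states that it is not meant for lymphoma studies, so this supports the proposed fix but does not establish the defect. The conflict inside Appendix 5 does that by itself.

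**Effect on the reported results:**

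- *CR changed to PR.* ORR counts CR + PR, so the numerator changes by −1 + 1 = 0 and the denominator is unchanged. ORR is unaffected. The CR row of the BOR table falls by one and the PR row rises by one.
- *Size of one reclassification, for illustration.* Group 1 cohorts under the 3+3 design have 3 to 6 subjects. If one subject in such a cohort is reclassified, the CR percentage moves by 1/6 ≈ 17 to 1/3 ≈ 33 percentage points.
- *Number affected.* SAP 1.3 reports 33 subjects enrolled in total. The number with lymphoma, and the number with an unassessed non-index lesion, are not given. No overall magnitude can be computed.

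**The case against.** The strongest reply is that the note does not authorize CR. The CR definition requires every criterion, the NE condition for inadequate or missing images sits directly above the note, and SAP 6.1.1.2 treats subjects with insufficient on-study tumor information as nonresponders. A careful assessor would withhold CR. This stands as far as it goes: CR is permitted by the note's literal wording but not compelled, so it cannot be said that the rule does inflate CR, only that it can. It does not remove the conflict, because the note says the opposite and no rule takes precedence.

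It is also fair to say that the consequence is limited. The primary endpoint is DLT incidence, Protocol 8.5 only lists ORR and PFS, and SAP 3.5 says there is no formal testing.

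A reader might infer several stronger points that the documents do not support:

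- *The trial applies opposite missing-lesion rules by tumor type.* This is so only for CR. RECIST Table 1 keeps PR and SD when non-target lesions are not all evaluated, and PD can be assigned on available evidence in both systems. Appendix 5 also says that its criteria were modified for the diseases under study.
- *PR is invalid whenever a non-index lesion is unassessed.* The PR criterion on non-index growth is unverified in that case, but allowing PR is an accepted convention in the RECIST table and is the category proposed here.
- *The progression date moves later.* SAP 6.1.1.1 dates progression when it is first identified. Growth in an unassessed lesion would be found at a later assessment whether the earlier visit was labeled SD, PR or NE.
- *Half the recorded lesions may be unseen at a CR.* With 6 index and 6 non-index lesions, 6/12 is a theoretical ceiling. It requires every index lesion to be assessed and every non-index lesion to be missed without the images counting as inadequate.

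**Conclusion.** The concern holds for complete response. The note and the CR definition in Appendix 5 contradict each other, and the same data can be classed as CR, not CR, or NE. The lymphoma CR count in the BOR table can therefore be overstated.

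The effect is confined to CR versus PR in a descriptive endpoint, if the case is resolved as PR as proposed below; ORR then does not change. The conclusion rests on two assumptions: that some lymphoma subjects have non-index disease recorded at baseline, and that at least one such lesion goes unassessed at a visit otherwise meeting CR. The documents do not show how often either occurs, so the practical effect may be small or nil. The point is still worth settling, because it concerns a stated rule that can give a wrong category.

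**What to change.** In Protocol Appendix 5, Non-Evaluable, replace the sentence on missing non-index lesions with:

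*If any non-index lesion present at baseline is not assessed at a time point, CR may not be assigned; the response is PR at best if the index criteria are met and no PD is seen. PD may still be assigned on available evidence.*

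Carry the same rule into SAP 6.1.1.2, so that BOR is derived consistently. If the SAP is already final, SAP Section 1 provides for later changes to be documented in the clinical study report.

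No change to the PFS rules is proposed. Flagging such visits as incomplete would raise the question of whether they count toward the SAP's censoring rule for two or more consecutive missing assessments, and nothing here requires that to be opened.

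The cost is one replaced passage in the protocol, one line in the SAP, and possibly a slightly lower CR count.

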Appendix 6. Common Terminology Criteria for Adverse Events (CTCAE) v4.03

CTCAE v 4.03 can be accessed from the below link:

<http://www.hrc.govt.nz/sites/default/files/CTCAE%20manual%20-%20DMCC.pdf>

Appendix 7. Pregnancy Precautions, Definition for Female of Childbearing Potential, and Contraceptive Requirements

1) Definitions

a. Definition of Childbearing Potential

For the purposes of this study, a female born subject is considered of childbearing potential following the initiation of puberty (Tanner stage 2) until becoming post-menopausal, unless permanently sterile or with medically documented ovarian failure.

Except in Group 2, subjects with breast cancer who are also receiving hormonal therapies, women are considered to be in a postmenopausal state when they are ≥ 60 years of age with cessation of previously occurring menses for ≥ 12 months without an alternative cause. In addition, women of any age with amenorrhea of ≥ 12 months may also be considered postmenopausal if their follicle stimulating hormone (FSH) level is in the postmenopausal range and they are not using hormonal contraception or hormonal replacement therapy.

Permanent sterilization includes hysterectomy, bilateral oophorectomy, or bilateral salpingectomy in a female subject of any age.

In addition, Group 2 subjects (breast cancer) who are pre/perimenopausal women are considered in a postmenopausal state due to treatment with the LHRH agonist goserelin. Patients must have commenced treatment with goserelin or an alternative LHRH agonist at least 4 weeks prior to first dose of study drug, leading to a reduction in luteinizing hormone production and consequent reduction of sex steroid hormones to castration levels by the time of exposure to study drugs.

b. Definition of Male Fertility

For the purposes of this study, a male born subject is considered to be fertile after the initiation of puberty unless permanently sterile by bilateral orchidectomy or medical documentation.

2) Contraception Requirements for Female Subjects

a. Study Drug Effects on Pregnancy and Hormonal Contraception

GS-5829 is contraindicated in pregnancy as any potential for human teratogenicity/fetotoxicity in early pregnancy is currently unknown. GS-5829 has insufficient data to exclude the possibility of a clinically relevant interaction with hormonal contraception that results in reduced contraception efficacy. Therefore, contraceptive steroids are not recommended as a contraceptive method either solely or as a part of a contraceptive regimen. Please refer to the latest version of the investigator's brochure for additional information.

b. Contraception Requirements for Female Subjects of Childbearing Potential

The inclusion of female subjects of childbearing potential requires the use of highly effective contraceptive measures. They must also not rely on hormone-containing contraceptives as a form of birth control during the study. They must have a negative serum pregnancy test at Screening and a negative pregnancy test on the Baseline/Day 1 visit prior to initial randomization. Pregnancy tests will be performed at protocol-specified dates thereafter. Female subjects must agree to one of the following from Screening until 30 days following the end of relevant systemic exposure.

- Complete abstinence from intercourse of reproductive potential. Abstinence is an acceptable method of contraception only when it is in line with the subject's preferred and usual lifestyle.

Or

- Consistent and correct use of 1 of the following methods of birth control listed below.
 - Intrauterine device (IUD) with a failure rate of <1% per year
 - Tubal sterilization
 - Essure micro-insert system (provided confirmation of success 3 months after procedure)
 - Vasectomy in the male partner (provided that the partner is the sole sexual partner and had confirmation of surgical success 3 months after procedure)

Female subjects must also refrain from egg donation and in vitro fertilization during treatment and until at least 30 days after the end of relevant systemic exposure.

3) Contraception Requirements for Male Subjects

It is theoretically possible that a relevant systemic concentration may be achieved in a female partner from exposure of the male subject's seminal fluid. Therefore, male subjects with female partners of childbearing potential must use condoms during treatment and until 90 days after the end of relevant systemic exposure. Additional contraception recommendations should also be considered if the female partner is not pregnant.

Male subjects must also refrain from sperm donation during treatment and until at least 90 days after the end of relevant systemic exposure.

4) Unacceptable Birth Control Methods

Birth control methods that are unacceptable include periodic abstinence (e.g., calendar, ovulation, symptothermal, post-ovulation methods), withdrawal (coitus interruptus), spermicides

only, and lactational amenorrhea method (LAM). Female condom and male condom should not be used together.

5) Procedures to be Followed in the Event of Pregnancy

Subjects will be instructed to notify the investigator if they become pregnant at any time during the study, or if they become pregnant within 30 days of last study drug dose. Subjects who become pregnant or who suspect that they are pregnant during the study must report the information to the investigator and discontinue study drug immediately. Subjects whose partner has become pregnant or suspects she is pregnant during the study must report the information to the investigator. Instructions for reporting pregnancy, partner pregnancy, and pregnancy outcome are outlined in Section [7.6.2.1](#).

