7.6.2. Instructions for Reporting Special Situations

7.6.2.1. Instructions for Reporting Pregnancies

The investigator should report pregnancies in female study subjects that are identified after initiation of study medication and throughout the study, including the post study drug follow-up period, to Gilead DSPH using the pregnancy report form within 24 hours of becoming aware of the pregnancy. Refer to the eCRF completion guidelines for full instructions on the mechanism of pregnancy reporting.

The pregnancy itself is not considered an AE nor is an induced elective abortion to terminate a pregnancy without medical reasons.

Any premature termination of pregnancy (eg, a spontaneous abortion, an induced therapeutic abortion due to complications or other medical reasons) must be reported within 24 hours as an SAE. The underlying medical reason for this procedure should be recorded as the AE term.

A spontaneous abortion is always considered to be an SAE and will be reported as such. Furthermore, any SAE occurring as an adverse pregnancy outcome post study must be reported to Gilead DSPH.

The subject should receive appropriate monitoring and care until the conclusion of the pregnancy. The outcome should be reported to Gilead DSPH using the pregnancy outcome report form. If the end of the pregnancy occurs after the study has been completed, the outcome should be reported directly to Gilead DSPH.

Pregnancies of female partners of male study subjects exposed to Gilead or other study drugs must also be reported and relevant information should be submitted to or Gilead DSPH using the pregnancy and pregnancy outcome forms within 24 hours. Monitoring of the subject should continue until the conclusion of the pregnancy. If the end of the pregnancy occurs after the study has been completed, the outcome should be reported directly to Gilead DSPH.

Gilead DSPH: Fax: PPD
Email: PPD

Refer to [Appendix 7](#) for Pregnancy Precautions, Definition for Female of Childbearing Potential, and Contraceptive Requirements.

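### A man's duty to report a partner's pregnancy is tied to the study period, while the protocol's own male precautions run 90 days past exposure and investigator reporting has no end date

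*Protocol*

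**What the plan says.** **Male precautions (Protocol, Appendix 7, items 3 and 4).** Men with partners of childbearing potential "must use condoms during treatment and until 90 days after the end of relevant systemic exposure". In addition: "Male subjects must also refrain from sperm donation during treatment and until at least 90 days after the end of relevant systemic exposure". The reason given is that a relevant concentration could, in theory, reach a partner through seminal fluid.

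**Male notification (Appendix 7, item 5).** "Subjects whose partner has become pregnant or suspects she is pregnant during the study must report the information to the investigator". Nothing is added for the time after the last dose.

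**Female precautions and notification (Appendix 7, items 2b and 5).** "Female subjects must agree to one of the following from Screening until 30 days following the end of relevant systemic exposure". A woman's duty to inform the site applies "if they become pregnant at any time during the study, or if they become pregnant within 30 days of last study drug dose".

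**Investigator to sponsor (Sections 7.6.1 and 7.6.2.1).** Section 7.6.1 describes a pregnancy report as covering female subjects and the partners of men who are on study. Section 7.6.2.1, to which item 5 refers for reporting instructions, covers female subjects' pregnancies "identified after initiation of study medication and throughout the study, including the post study drug follow-up period". It makes partner pregnancies of exposed men reportable within 24 hours and sets no end date for them. It also requires outcomes that fall after the study, and post-study SAEs that are adverse pregnancy outcomes, to go to the sponsor's safety group.

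**Last contact (Synopsis; Section 6.4.1).** Safety follow-up lasts 30 days after treatment stops. The closing telephone call is 30 days (± 7) after the last dose, and its stated purpose is to ask about adverse events.

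**The concern.** A pregnancy in a subject's partner reaches the investigator mainly because the subject reports it. The protocol places a time limit on that step and none on the step that depends on it. The time limit also appears to fall well inside the window for which the protocol itself asks men to take precautions. Women are given a notification tail after the last dose; men are given none.

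The 30-day contact does not obviously close the gap. It asks about adverse events, and Section 7.6.2.1 says that a pregnancy is not itself an adverse event. A partner pregnancy conceived in the second or third month after the last dose would lie beyond that contact in any case.

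What is at stake is the completeness of pregnancy follow-up in a first-in-human study. Appendix 7 says that the human teratogenic potential of GS-5829 is unknown, and Section 1.2.2.2 lists the male reproductive system among the target organs in mice and dogs. If adverse outcomes can come in after the study by a separate route while uneventful pregnancies are not solicited, the adverse outcomes cannot be set against all conceptions in the window.

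**Working it through.** The plan states no figure to reproduce. The check is a comparison of windows, in days after the last dose.

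**Inputs**
- W: days from last dose to the end of relevant systemic exposure. Neither W nor a half-life value is given.
- Male precautions end at W + 90 (Appendix 7, items 3 and 4).
- Female contraception ends at W + 30 (Appendix 7, item 2b).
- Female notification ends at day 30 (Appendix 7, item 5).
- Male notification ends with the study (Appendix 7, item 5). The phrase is not defined. Assumption: for an individual subject it ends at the safety contact, day 30 (± 7).

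**Men.** Gap = (W + 90) − 30 = 60 + W days.
- Contact at day 37: 90 + W − 37 = 53 + W.
- Contact at day 23: 90 + W − 23 = 67 + W.
- With W = 0 the gap is 60 of 90 days, two thirds of the male window.

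**Women.** Gap = (W + 30) − 30 = W days. Both windows are 30 days long; only the starting point differs.

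**Illustration of W.** Assume that relevant exposure ends after five half-lives and that the half-life lies between 6 and 48 hours. Neither assumption comes from the documents. Then W = 5 × 6 / 24 = 1.25 days to 5 × 48 / 24 = 10 days.

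| | W = 0 | W = 1.25 | W = 10 |
|---|---|---|---|
| Men, contact at day 30 | 60 | 61.25 | 70 |
| Men, contact at day 37 | 53 | 54.25 | 63 |
| Men, contact at day 23 | 67 | 68.25 | 77 |
| Women | 0 | 1.25 | 10 |

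The male result depends little on W, because the 60 days come from the stated 90 and the 30-day contact. The female result is W and nothing else, so the assumption fixes it entirely.

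**Counting basis.** Item 5 counts women who become pregnant within its window, whereas Section 7.6.2.1 counts pregnancies that are identified within its own. A pregnancy conceived late in a window is usually recognised after it, so the two rules can classify the same case differently.

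**The case against.** The strongest reply is that Section 7.6.2.1 is the operative text. Item 5 of Appendix 7 refers to it, it sets no end date for partner pregnancies, it follows pregnancies to their conclusion, and it captures adverse outcomes and late deliveries after the study. Section 7.3.3 adds that relevant SAEs learned of after participation must be reported. This stands. A reader might infer that pregnancy reporting stops, or that these conceptions go unreported; the documents support neither. They support only that the subject has no stated duty to notify for part of the window, so that some pregnancies may not become known. Section 7.6.2.1 cannot act on what the investigator has not been told, and Section 7.3.3 does not oblige investigators to seek events actively after 30 days.

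Other limits also stand:
- **End of study.** The only definition of study completion (Section 9.1.1, on financial disclosure) is for the trial as a whole. Appendix 5 asks for follow-up at roughly 8-week intervals for lymphoma subjects who stop before progression. For some men the gap could be shorter than 60 + W days.
- **Women.** A reader might infer a gap comparable to the male one. The documents show only different starting points.
- **Exposure.** A reader might take the 90 days as a period that the sponsor regards as exposed. The window begins after relevant exposure has ended, and the rationale is worded as theoretical. The animal findings in men's target organs concern fertility, and Section 1.5 calls the effects on the male tract reversible.
- **Sole source.** A reader might infer that this trial is the only source of pregnancy data. Section 1.2.3 names a concurrent GS-5829 trial in prostate cancer.
- **Subject instructions.** The consent pages are not available, so what men were actually told cannot be checked.
- **Scale.** SAP Section 1.3 records 33 subjects in all, and Group 2 is limited to women in a postmenopausal state. The documents do not give the number of men with partners of childbearing potential, but few conceptions would be expected.

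**Conclusion.** The concern holds as an inconsistency between passages. Appendix 7, item 5, and Section 7.6.1 tie partner-pregnancy reporting to the study, while the male precautions run to 90 days after relevant exposure and Section 7.6.2.1 is open-ended. On the assumption that the study ends for a subject at the 30-day contact, the man has no stated duty to notify for 60 + W days (53 + W to 67 + W with the call window). Partner pregnancies conceived then may be missed, although any that become known are reportable.

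For female subjects the finding is limited to the different starting points, and the size of that gap cannot be determined from the documents.

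The matter concerns safety reporting only. The DLT endpoint, the sample size and every planned analysis are unaffected.

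**What to change.** - Reconcile Appendix 7, item 5, with Sections 7.6.1 and 7.6.2.1, so that the subject's duty to notify and the investigator's duty to report both cover the contraception windows that the protocol already sets, for men's partners and for female subjects, counted by date of conception.
- State in days after the last dose when relevant systemic exposure ends. Half-life is already a planned PK parameter (Section 8.1.3), so the basis can come from the study's own data.
- Remind subjects of the notification duty at the end-of-treatment visit and at the 30-day contact.

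The cost is a few sentences in the protocol and the subject instructions. The existing pregnancy and outcome forms serve, no visit or test is added, and the contraception rules stay as they are. The one downside is a small amount of passive reporting after the last visit.
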